### **3.e.2 Screening Log**

See Appendix

### **3.e.2 Eligibility Criteria**

All participants must meet the following criteria:

- between the ages of 40 and 75 years old
- All knee OA participants must exhibit symptomatic knee OA, which we will define as a normalized, person based, Western Ontario and McMaster Universities Arthritis Index (WOMAC) function subscale score > 31(out of 100 points, indicating most dysfunction)
- radiographic evidence of tibiofemoral OA (2-4 on the Kellgren – Lawrence scale) 39
- neuromuscular activation deficits, defined as quadriceps neuromuscular activation of less than 90% in the involved leg.

Potential participants meeting any of the following criteria (based on the electronic medical record or in laboratory screening) will be excluded if:

- Diagnosed with a cardiovascular condition restricting exercise
- Have had a corticosteroid or hyaluronic acid injection in the involved knee in the previous 6-months
- Have pacemaker
- Have a neurodegenerative condition
- Have rheumatoid arthritis

- Have cancer
- Have a neural sensory
- Have dysfunction over the knee
- Have a Body Mass Index (BMI) over 35
- Have a history of lower extremity orthopaedic surgery in the past year
- Have a history of a traumatic knee injury in the past 6 months
- Have any history of a total knee arthroplasty in either extremity
- Have a diagnosed, non-reconstructed knee ligament tear.
- Need an assistive device to walk
- Currently pregnant

### **3.f Informed Consent and HIPPA**

#### **3.f.1 Informed Consent Process**

Once a potential subject meets the telephone screening criteria for eligibility, and is interested in participating, he/she will be asked to meet a study team member at the Sports Medicine Research Laboratory to begin the consenting process.

We will use a University of North Carolina Health System IRB approved consent form with included language that satisfies the HIPAA requirements and outlines the protection of health information utilized in the study.

Informed consent will be obtained by a study team member in the Sports Medicine Research Laboratory in a private space. The study team member will read the IRB approved consent form to the potential subject, and provide an opportunity for him/her to ask any questions that they may have about the research study. We anticipate this process to take approximately 20 minutes, but this time will not be limited should a subject have additional questions or concerns regarding the study. During this phase of the consent process, it will be stressed that the subject is not obligated to participate in the study, that participation is completely voluntary, and that he/she may withdrawal from the study at any time without penalty. Also, potential risks from participating in the study are outlined in the consent form, as are the measures taken to protect against study specific risks.

During explanation of the TENS device, the investigator will describe TENS as a stimulus that is felt as tingly to some people will others report no feeling or have a “sub-sensory response”.

Once the information in the consent form is fully reviewed and understood by the subject, he/she will be asked to decide at that time if they would like to voluntarily participate in the research study. If the subject does choose to participate in the study, both the subject and the study team member will sign and date the consent form. In addition, each page of the consent form must be initialed by the subject. Each enrolled participant will then receive a signed copy of their consent form to keep for their records.

If after reviewing the consent form, subjects are not sure they would like to participate in the study at this time, they may choose to consider the study further at home, and then contact the study team if they decide later that they would like to participate.

Subjects will only be included if they have capacity to give legally effective consent.

The original signed consent forms will be kept in each subject’s individual study folder. These folders will be stored in a locked file cabinet in a locked cabinet of the neuromuscular research laboratory.

#### **3.f.2 Informed Consent Form**

See Appendix B for Approved Consent form

### **3.f.3 HIPPA Authorization**

The privacy and confidentiality of research participants are to be respected and protected at all times. This research study will comply with the HIPAA Privacy Rule as well as all other state, federal, and institutional regulations intended to protect the rights, safety, and welfare of human participants involved in research studies. We will attempt to minimize the collection, storage, and transmission of information containing patients' personal identifiers, and, whenever identifiers are necessary, protect against unauthorized access or disclosure. In addition, we will employ several rigorous procedures for protecting against risks to participant privacy and confidentiality of data. We will only collect and store information about study participants that is relevant to the research as outlined in the protocol. We will minimize the use of paper documents by entering the majority of study data directly into secure computer databases. All study databases will be password protected and only study team members whose job functions require access to these data will have permissions. Whenever possible, data will not be stored on laptop computers. Individual patient data will not be shared with individuals outside the study team, except as required by law and/or for regulatory purposes.

All study staff must regularly fulfill certification requirements in Human Subjects Protection training. Study personnel are also regularly trained in stringent computer and information security procedures. All electronic study data will be securely backed up on a nightly, monthly, and biannual schedule.

Research study records will be maintained for no less than 7 years following the completion of the study, after which time personal identifying information will be removed. Research information in a subject's medical record will be kept indefinitely.

### **3.g Study Intervention**

#### *Intervention Overview*

The current study is a **Phase 1 clinical trial** that will have three randomized groups. All groups will receive the same supervised, standardized TE program at the UNC Meadowmont Physical Therapy Clinic. *TENS+TE* and *sham TENS+TE* patients will be instructed to utilize their device during all 12 physical therapy sessions as well as 8 hours per day when they are the most active for 4-weeks (28 days). Twelve TE sessions over 4 weeks is the current standard of care for patients with knee OA at the UNC Meadowmont Physical Therapy Clinic. Additionally, previous data indicate strong effect sizes for neuromuscular improvements following a 12 session/4-week intervention. Patients included in this study will be treated by 1 of 4 physical therapists (PT) associated with this study during each session (see participating physical therapists listed below). Patients in all groups will receive TE for their involved leg 3 times per week for 4 weeks (12 sessions). The PTs will review each patient's medical history and physician instructions before starting TE. A PT will conduct a lower extremity physical assessment prior to beginning rehabilitation and following the 4-week intervention for clinical use. *The overall goals of the TE program are to increase lower extremity strength and function.* Progressive exercise will be similar to that previously reported by the PI. Procedural reliability of the intervention will be maximized using: 1) training sessions for the PTs to ensure all exercises are taught and progressed in the same manner, 2) tracking compliance of *TENS/ sham TENS+TE*, 3) biweekly review patient charts regarding exercises, and 4) biweekly evaluation of therapeutic exercise delivery on a subset of patients at random time points using a rubric. Lower extremity strengthening will be progressed through open and closed chain strengthening (see exercises in tables X-X). Range of motion limitations and soreness will be addressed or managed with stretching, manual therapy, and/or cryotherapy. All strengthening exercises will be systematically progressed, on an individual basis, using the daily adjustable progressive resistive exercise system. Functional exercises will be progressed according to the patients' ability and any reactive inflammation from TE.

**The Experimental TENS Group (*TENS+TE*):** Patients assigned to the TENS+TE group will receive a *Select System TENS unit (EMPI, Inc., St. Paul, MN)*, self-adhesive electrodes and batteries upon admission into the clinical trial and allocation into the TENS +TE group. TENS+TE patients will meet with a member of the study team in a private room at the Proaxis clinic prior to the initial visit with the PT. Patients will be taught how to apply the electrodes on the knee joint and educated on how to operate the TENS unit. An instruction manual will be provided to the patients for reference purposes explaining device operation and a reminder for how to escalate dosing parameters; these dosing parameters were successfully used in our pilot study. Patients will be provided with the phone number of an unblinded member of study team to call with questions. The primary method of collecting TENS compliance will be using a digital memory chip built into the TENS units that records the length of time each participant uses the device. Patients will log the hours of daily use as a backup.

**The Sham Group (*sham TENS+TE*):** Sham TENS+TE patients will receive a *Select System TENS unit (EMPI, Inc., St. Paul, MN)* specifically configured to cease TENS current output 20 seconds after the participants initiation. For blinding purposes, patients will be told that they should feel a brief stimulation (~20 seconds) that will become “sub-sensory” in nature. In reality, the Sham TENS unit will emit no current after 20 seconds. The sham TENS unit will have a functioning display identical to the active TENS units indicating the sham output voltage. The instruction manual that the sham group receives will not have any dose escalating procedures.

**The Comparison Group (*TE only*):** The role of the comparison group is to provide data on how traditional TE affects the outcome measures. The TE only group will allow us to assess how the addition of TENS and sham TENS to traditional TE will augment the effects of traditional TE. The TE only group will receive exactly the same TE as the TENS+TE and the sham TENS+TE in order to specifically determine what changes are attributed to TE only and not the neuromuscular changes brought about by *TENS+TE* or *sham TENS+TE*.

## **Transcutaneous Electrical Nerve Stimulation (TENS)**

The Empi Select TENS unit has 510k approval (K090922) for use in the management of “symptomatic relief and management of chronic, intractable pain and relief of pain associated with arthritis”. The Empi TENS unit is a battery powered single –function device to provide simple modulated pulse therapy. We will be using the TENS unit in the same capacity in patients with knee osteoarthritis.

## **TENS and Sham TENS Therapies**

An unblinded investigator will meet the study participant in a private treatment room in the Meadowmont Physical Therapy clinic 20-minute before the first therapeutic exercise session. Patients will be provided information about applying electrodes, charging batteries, increasing and maintaining the TENS. Study participants will be provided time to ask questions and business cards with the telephone numbers and email addresses for the unblinded study investigators. The TENS units will all come with a manual as well as a short “How to Work Your Empi TENS Unit” manual. The instructions will be slightly different for the Active TENS and Sham TENS units.

## **Knee-habilitation Study Guide – ACTIVE TENS**

### **How to work your Empi TENS Unit**

The Empi TENS unit is configured by the study team to output the proper TENS treatment to your knee. You will be responsible for this 4-step process:

- 1) Applying the TENS electrodes on your knee correctly
- 2) Ensuring that charged batteries are in the TENS units
- 3) Increasing the stimulus to the correct intensity
- 4) Maintaining a proper dose of TENS throughout the day

### **Applying the TENS Electrodes**

Before putting TENS electrodes on your skin make sure that your skin is clean (free from oils, dirt or lotions). Remove the sticky portion from the clear plastic backing and apply around the outer portions of your kneecap. Keep the electrodes off of your thigh and leg muscles, thereby focusing the TENS treatment on the front of the knee. The red electrodes and the black electrodes should be crossed in the fashion shown below. After a day of use the electrode can be stored on the same clear plastic backing.

### **Ensuring that Charged Batteries are in the TENS Units**

It is important that the batteries are charged at the beginning of the day. Store the batteries in the charger at night. A red light on the charger indicates that the batteries are not fully charged. A green light on the charger indicates that the batteries are charged. Charged batteries should be removed from the charger and placed in the TENS unit in the morning. You will receive multiple sets of batteries that can be recharged and used in the TENS unit. The TENS unit will indicate if it is low on battery life; please change the batteries and recharge at this time. If for some reason you need new AAA batteries, please notify the study personnel who can supply these to you.

### **Increasing the TENS Stimulus to the Correct Intensity**

First turn on the TENS unit with the middle button that is marked: "on/off". Next increase channels 1 and 2 slowly until you achieve a strong sensory tingling feeling in your knee. You should LOWER the stimulation if you feel your muscles contracting or you feel discomfort in your knee. You should increase (HIGHER) the stimulation if you do not feel a tingling feeling around the knee. We would like you to increase the stimulation to a point where you feel a strong but comfortable stimulation.

### **Maintaining a Proper TENS Dosage**

Some people may accommodate to the stimulation minutes to hours after applying the stimulus. If you accommodate to the stimulation we would like you to increase the intensity of the stimulation with the button marked "HIGHER" until a strong but comfortable stimulation is felt.

## **Knee-habilitation Study Guide – Sham TENS**

### **How to work your Empi TENS Unit**

The Empi TENS unit is configured by the study team to output the proper TENS treatment to your knee. You will be responsible for this 4-step process:

- 1) Applying the TENS electrodes on your knee correctly
- 2) Ensuring that charged batteries are in the TENS units
- 3) Increasing the stimulus to the correct intensity
- 4) Maintaining a proper dose of TENS throughout the day

### **Applying the TENS Electrodes**

Before putting TENS electrodes on your skin make sure that your skin is clean (free from oils, dirt or lotions). Remove the sticky portion from the clear plastic backing and apply around the outer portions of your kneecap. Keep the electrodes off of your thigh and leg muscles, thereby focusing the TENS treatment on the front of the knee. The red electrodes and the black electrodes should be crossed in the fashion shown below. After a day of use the electrode can be stored on the same clear plastic backing.

### **Ensuring that Charged Batteries are in the TENS Units**

It is important that the batteries are charged at the beginning of the day. Store the batteries in the charger at night. A red light on the charger indicates that the batteries are not fully charged. A green light on the charger indicates that the batteries are charged. Charged batteries should be removed from the charger and placed in

the TENS unit in the morning. You will receive multiple sets of batteries that can be recharged and used in the TENS unit. The TENS unit will indicate if it is low on battery life; please change the batteries and recharge at this time. If for some reason you need new AAA batteries, please notify the study personnel who can supply these to you.

### **Increasing the TENS Stimulus to the Correct Intensity**

First turn on the TENS unit with the middle button that is marked: "on/off".

Next increase channels 1 and 2 slowly until you feel a tingly feeling around your knee. Some people may accommodate to the stimulation, meaning you may not feel any tingly feeling, within one minute of applying the stimulus. Please keep the stimulation intensity between 3 and 5 at all times. Remember to check and make sure throughout the day that the stimulator is indicating that TENS is being delivered to your knee, if the TENS unit is not one try pushing "on" or "changing the batteries".

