**Long Arc Knee Flexion-** Knee flexion will be performed seated on a table with knees extended. The lever arm will be adjusted to have the foam pad make contact with the leg approximately one-third of the way up the distal calf on the posterior side. Patients will be instructed to flex the knee until ~90° is achieved and patients "squeeze the hamstrings" for a 1-2 second hold. If patients experience knee pain the therapist should adjust the arc of knee flexion motion to a point that minimizes pain. The weight should then be lowered to the resting position in approximately 2-3 seconds. Weights can be added to the table and the DAPRE system will be used to progress weight.

**Heel Raises –** Patients will stand next to a plinth and be allowed to use the plinth for balance. They will be instructed to raise their heels off the ground over a 2 second period until they are on their toes. The patients will be instructed to hold this position for 2 seconds and lower slowly over a two second period. Patients should progress to the next phase if they complete two sets in a row without increased knee pain and body mechanics are deemed within normal by the therapist. The patients can be progress to one limb and then by using weight in the contralateral hand (increasing in 5lb increments).

**Ball Squats-** The physical therapist will determine the appropriate sized physio-ball to be used in this exercise based on the size of the patient. The physio-ball will be placed at the lumbar spine of each patient between their back and the wall. The patient will keep arms at their side or crossed over the chest and their feet shoulder width apart and in front of them enough that during the squat the knees do not move anterior to the toes. The patients will squat as far as they feel comfortable aiming for between ~45 to 90° of knee flexion. The

concentric and eccentric phases of the exercise should be controlled and last 3-4 seconds in each direction with a 1-2 second hold at maximum knee flexion.

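### Different intensity rules for active and sham TENS, with an uncovered display at supervised sessions, could let therapists sometimes infer the active arm; their blinding status is not stated

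*Combined protocol and SAP*

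**What the plan says.** All points are from the combined protocol and SAP.

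- **Sham rule.** The sham patient guide (3.g) says "Please keep the stimulation intensity between 3 and 5 at all times". The Intervention Overview adds: "The instruction manual that the sham group receives will not have any dose escalating procedures".
- **Active rule.** Active patients are asked to "increase the stimulation to a point where you feel a strong but comfortable stimulation". Later in the day the guide says "If you accommodate to the stimulation we would like you to increase the intensity of the stimulation with the button marked" HIGHER. No numeric range or ceiling is given.
- **Display.** "The sham TENS unit will have a functioning display identical to the active TENS units indicating the sham output voltage".
- **Setting.** Both device arms use the unit at all 12 clinic sessions. Physical therapists teach, supervise and progress the exercise there (3.g, Therapeutic Exercises).
- **Progression.** "All strengthening exercises will be systematically progressed, on an individual basis, using the daily adjustable progressive resistive exercise system". Step-ups and heel raises advance after two consecutive sets without more knee pain, provided "body mechanics are deemed within normal by the therapist".
- **Common programme.** "The TE only group will receive exactly the same TE as the TENS+TE and the sham TENS+TE".
- **Blinding.** Section 3.h names outcome evaluators and device-arm patients as blinded, lists the unblinded staff by function, and undertakes to keep other staff who collect data blind. Therapists are not mentioned. The Data and Safety Officer section has the therapists collect all adverse events.
- **Access to the manual.** Section 3.t sends each new version to the whole study team and keeps a binder open to all study staff.

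**The concern.** The sham arm protects one contrast, TENS+TE against sham TENS+TE. That contrast isolates TENS only if everything else is delivered alike. The people who decide how fast each patient's exercise advances work beside the unit at every session, and the two arms run it under different rules. If a therapist forms a view about who is on active TENS, progression, encouragement, manual therapy or cryotherapy could drift between the arms. A difference in quadriceps activation or function could then arise partly from exercise. The same cue could colour how adverse events are elicited and recorded. The issue is confined to active versus sham: TE-only patients carry no unit and are recognisable to the therapist anyway.

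**Working it through.** The plan has no figure of its own to reproduce here. N=90 is given without alpha, power, effect size, SD or dropout. The check is mainly a comparison of sections.

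**Step 1. What a therapist could see, and what it would tell.** This assumes that the intensity numbers in the sham guide are what the display shows, and that patients follow their guide.

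| Observation in a session | Active guide | Sham guide | Information |
|---|---|---|---|
| Turning up at switch-on | yes | yes, until tingling is felt | none |
| Reading of 3 to 5 | possible, no range given | expected | does not identify sham |
| Reading above 5 | allowed | outside the guide | points to active |
| Repeated increases after set-up | requested on accommodation | not requested | suggests active |
| Pressing on again or changing batteries | possible | requested if the unit has stopped | none |

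The active guide says that accommodation may begin within minutes, so an increase can fall inside a 45-minute session. The cue works in one direction and only some of the time. Conversation is a second route: sham output stops 20 seconds after the patient starts the unit, so the arms would describe sensation differently.

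**Step 2. Who holds the key.** The roster in 3.c lists the treating clinicians among study staff. The exercise descriptions they need are in 3.g, which also holds both device guides and the sham specification. Section 3.t opens the whole manual to all staff, which includes the blinded outcome assessors.

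**Step 3. Are therapists meant to be blind?** Not stated. Three things suggest it: they are absent from the unblinded list in 3.h, they collect adverse events and so come within the wording about data collectors, and device teaching takes place in a private room. This is an inference from the text.

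**Step 4. How much discretion remains.** Strengthening follows a named progression system, step heights and weight increments are fixed, and balance advances on a count of touch-downs. Judgement remains in the body-mechanics criterion, in functional exercise guided by ability and inflammation, in limiting the range of motion for pain, and in the adjunct treatments.

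**Step 5. Would the data show a difference?** Compliance data in 3.i.2 count sessions and device use. Charts are reviewed biweekly, a rubric is applied to a subset of patients, and delivery is observed monthly (3.g, 3.m, 3.p.3). None of these is described as blind to arm or as comparing delivered exercise between arms.

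**Step 6. Illustration of consequence.** Assume a true TENS effect of zero, two-sided alpha 0.05 (z = 1.96), n per arm, a normal approximation, and an exercise-driven shift of b SD in one arm:

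P(reject) = 1 − Φ(z − b/√(2/n)) + Φ(−z − b/√(2/n)).

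For n = 90/3 = 30 (equal split assumed), √(2/30) = 0.258. At b = 0.2 the standardised shift is 0.2/0.258 = 0.775, and P = 0.118 + 0.003 = 0.121.

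| b (SD) | n = 30 | n = 24 |
|---|---|---|
| 0 | 5.0% | 5.0% |
| 0.1 | 6.7% | 6.4% |
| 0.2 | 12.1% | 10.7% |
| 0.3 | 21.3% | 18.0% |

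n = 24 is an assumed 20% loss (30 × 0.8). The documents give no basis for choosing any value of b.

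**The case against.** The strongest reply is that the cue is weak and the discretion small. The display hardware is identical, active patients may well sit at 3 to 5, and no section says where the unit is worn or that therapists look at it. The progression system, therapist training, chart review, rubric and monthly observation all constrain what a therapist can do. Higher exercise load in the active arm could also be an effect of TENS. All of this stands. It limits the problem without closing it: the safeguards check fidelity to the exercise protocol, and none conceals the arm or compares the arms.

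Three stronger readings are tempting, and the documents do not support them.

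- A reader might infer that therapists can read allocation from the display. They can at most sometimes infer active. Nothing on the display proves sham.
- A reader might multiply an assumed 60 device patients by 12 sessions and speak of 720 sessions with the display in view. That product counts scheduled device sessions under an assumed equal split and full attendance. How often a display would be seen is unknown.
- A reader might say that individual progression contradicts the statement that TE-only patients receive exactly the same TE. Read with the Intervention Overview, it means the same programme, individually progressed in every arm. It does not promise equal load and needs no rewording.

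The exercise tables and the IRB protocol and intervention appendices are referred to but are not in the available text, so recording of exercise load cannot be ruled out.

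**Conclusion.** The point holds as a gap in the blinding plan that is cheap to close. Therapists' blinding status is unstated, the arm-specific intensity rules with an uncovered display could sometimes reveal the active arm, and the manual gives therapists and assessors the key. Performance bias in TENS versus sham, and ascertainment bias in adverse events, are therefore possible. Neither is demonstrated, and size and direction are unknown. The percentages above show only what a shift of a given size would do at about 30 per arm. The conclusion assumes that the display shows the intensity setting named in the sham guide, that patients follow their guides, and that therapists are meant to be blind between the device arms. If they are not, that should be stated and the limitation acknowledged.

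**What to change.** 1. In 3.h, state that therapists are to be blind between the two device arms.
2. During clinic sessions, keep the display covered or the unit in an opaque pouch, with the controls still within the patient's reach. Ask patients not to discuss settings or sensation with therapists or assessors.
3. Give therapists and assessors a copy of the manual without the sham specification and the two device guides. The unblinded staff keep the full version.
4. Extend the group-guess questionnaire, now completed by the patient and the investigator running the 8-week assessment, to the treating therapists.
5. From the charts already reviewed biweekly, tabulate exercise progression and adjunct treatment by arm. This is a descriptive check. By itself it cannot separate therapist bias from an effect of TENS on exercise tolerance, so it supports the concealment steps and does not replace them.

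The cost is minor materials, document control for a second copy of the manual, one short form and one descriptive table. No device setting or exercise rule is proposed or changed.
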